Annex 2. Patient Evaluation Form

DATE:

PATIENT EVALUATION FORM

NAME-SURNAME:

SEX:

BIRTH DATE/AGE:

HEIGHT:

WEIGHT:

BMI:

EDUCATION LEVEL:

MARITAL STATUS:

PHONE NUMBER:

NUMBER OF BIRTH:

TYPE OF BIRTH:

MENOPEASE STATUS:

WEEKLY ALCOHOL CONSUMPTION:/ week

WEEKLY TEA CONSUMPTION:/ week

WEEKLY CAFFEINE CONSUMPTION:/ week

MEDICAL HISTORY:

DRUGS USED:

Annex 3. Assessment of Muscle Strength

PERFECT SCHEME					
	Power (P)	Endurance (E)	Repetitions (R)	Fast Contraction (F)	Every Contraction Time (ECT)
1					
2					
3					
MEAN					

Surface EMG			
	Resting tone	Maximum Voluntary Contraction (MVC)	Pelvic Floor Muscle Endurance
1			
2			
3			
Mean			

Annex 4. International Consultation on Incontinence Questionnaire-Urinary Incontinence Short Form

Initial number

ICIQ-UI Short Form

CONFIDENTIAL

DAY MONTH YEAR

Today's date

Many people leak urine some of the time. We are trying to find out how many people leak urine, and how much this bothers them. We would be grateful if you could answer the following questions, thinking about how you have been, on average, over the PAST FOUR WEEKS.

1 Please write in your date of birth:

DAY MONTH YEAR

2 Are you (tick one):

Female Male

3 How often do you leak urine? (Tick one box)

- never 0
 about once a week or less often 1
 two or three times a week 2
 about once a day 3
 several times a day 4
 all the time 5

4 We would like to know how much urine you think leaks.

How much urine do you usually leak (whether you wear protection or not)?
 (Tick one box)

- none 0
 a small amount 2
 a moderate amount 4
 a large amount 6

5 Overall, how much does leaking urine interfere with your everyday life?

Please ring a number between 0 (not at all) and 10 (a great deal)

0 1 2 3 4 5 6 7 8 9 10
 not at all a great deal

ICIQ score: sum scores 3+4+5

6 When does urine leak? (Please tick all that apply to you)

- never – urine does not leak
 leaks before you can get to the toilet
 leaks when you cough or sneeze
 leaks when you are asleep
 leaks when you are physically active/exercising
 leaks when you have finished urinating and are dressed
 leaks for no obvious reason
 leaks all the time

Thank you very much for answering these questions.

Copyright © "ICIQ Group"

Annex 5. Urogenital Distress Inventory (UDI 6)

UROGENITAL DISTRESS INVENTORY (UDI 6)

Do you experience? If so how much are you bothered by:

	Not at all	A little bit	Moderately	Greatly
1. Frequent urination?	0	1	2	3
2. Urine leakage related to the feeling of urgency?	0	1	2	3
3. Urine leakage related to physical activity, coughing or sneezing?	0	1	2	3
4. Small amounts of urine leakage (that is drops)?	0	1	2	3
5. Difficulty emptying your bladder?	0	1	2	3
6. Pain or discomfort in the lower abdominal or genital area?	0	1	2	3

$$\frac{\text{RAW SCORE}}{6} \times 25 = \boxed{\text{FINAL SCORE}}$$

Annex 6. Incontinence Impact Questionnaire, Short Form (Iiq-7)

 OREGON HEALTH & SCIENCE UNIVERSITY Urology	Patient Name: _____ Date of Birth: _____ MRN: _____ Date of Service: _____ Physician: _____
---	---

Incontinence Impact Questionnaire, Short Form (IIQ-7)

Some people find that accidental urine loss may affect their activities, relationships, and feelings. For each question, circle the response that best describes how much your activities, relationships, and feelings are being affected by urine leakage over the past month.

Has urine leakage (incontinence) affected your:

	Not at All	Slightly	Moderately	Greatly
Ability to do household chores (cooking, housecleaning, laundry)?	0	1	2	3
Physical recreation such as walking, swimming, or other exercise?	0	1	2	3
Entertaining activities (movies, concerts, etc.)?	0	1	2	3
Ability to travel by car or bus more than 30 minutes from home?	0	1	2	3
Participation in social activities outside your home?	0	1	2	3
Emotional health (nervousness, depression, etc.)?	0	1	2	3
Feeling frustrated?	0	1	2	3

Adapted from Uebersax JS, Wyman FF, Shumaker SA, et al. Short forms to assess life quality and symptom distress for urinary incontinence in women: the incontinence impact questionnaire and urogenital distress inventory. *NeuroUrol Urodyn* 1995; 14: 131.

Annex 7. Assessment of Patient Satisfaction

1) How satisfied were you with the treatment you received?

05.....10
(Not satisfied at all) (Very satisfied)

2) How satisfied were you with the decrease in your complaints after your treatment?

05.....10
(Not satisfied at all) (Very satisfied)

3) How satisfied were you that your exercise program is followed by online interviews?

05.....10
(Not satisfied at all) (Very satisfied)

Annex 8. Assessment of Exercise Adherence

- Visual Analog Scale

How long did you adhere to the exercise program during your treatment?

05.....10

(Not satisfied at all)

(Very satisfied)

- Broome Pelvic Muscle Exercise Self Efficacy Scale

Question	Level of Confidence
Part A: How confident are you that you can:	
1. Contract your pelvic muscles?	0 10 20 30 40 50 60 70 80 90 100
2. Perform pelvic muscle contractions three times a day?	0 10 20 30 40 50 60 70 80 90 100
3. Perform pelvic muscle contractions while lying down?	0 10 20 30 40 50 60 70 80 90 100
4. Perform pelvic muscle contractions while standing?	0 10 20 30 40 50 60 70 80 90 100
5. Perform pelvic muscle contractions while sitting?	0 10 20 30 40 50 60 70 80 90 100
6. Contract your pelvic muscles without contracting your abdominal muscles?	0 10 20 30 40 50 60 70 80 90 100
7. Contract your pelvic muscles while washing fruits under running water?	0 10 20 30 40 50 60 70 80 90 100
8. Contract your pelvic muscles when lifting a bag of groceries?	0 10 20 30 40 50 60 70 80 90 100
9. Contract your pelvic muscles while standing at the sink brushing your teeth?	0 10 20 30 40 50 60 70 80 90 100
10. Contract your pelvic muscles rapidly?	0 10 20 30 40 50 60 70 80 90 100
11. Perform pelvic muscle contractions when you are sad?	0 10 20 30 40 50 60 70 80 90 100
12. Contract your pelvic muscles while showering after a busy and tiring day?	0 10 20 30 40 50 60 70 80 90 100
13. Perform pelvic muscle contractions when you are tired?	0 10 20 30 40 50 60 70 80 90 100
14. Contract your pelvic muscles when you awaken at night with a strong urge to urinate?	0 10 20 30 40 50 60 70 80 90 100
Part B: How confident are you that pelvic muscle contractions will prevent unwanted urine loss:	
1. When you experience a strong urge to urinate?	0 10 20 30 40 50 60 70 80 90 100
2. When you sneeze?	0 10 20 30 40 50 60 70 80 90 100
3. When you laugh?	0 10 20 30 40 50 60 70 80 90 100
4. While waiting 2 minutes for a restroom?	0 10 20 30 40 50 60 70 80 90 100
5. While waiting 5 minutes for a restroom?	0 10 20 30 40 50 60 70 80 90 100
6. When you wake up at night with a strong urge to urinate?	0 10 20 30 40 50 60 70 80 90 100
7. When you lift a heavy package?	0 10 20 30 40 50 60 70 80 90 100
8. When you cough?	0 10 20 30 40 50 60 70 80 90 100
9. When washing fruits and vegetables?	0 10 20 30 40 50 60 70 80 90 100

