Individuals with Urinary İncontinence applying to Göztepe [name]. Süleyman Yalçın Şehir Hastanesi will be invited to participate in the study. Individuals who volunteered to participate and whom met the criteria for participation will be randomized with simple random sampling method and will be

divided into two groups. In both groups participants will receive same exercise program and physiotherapist will follow up the exercise program every week by video conference method. While only the physiotherapist and the patient will take part in the one-on-one group, there will be a physiotherapist and 8 patients in the group sessions.

Inclusion Criteria

18-65 aged

BMI 18-30 kg/m²

Being diagnosed with stress incontinence or mixed incontinence (dominantly SUI)

Mild or moderate incontinence (mild SUI; urinary incontinence with coughing, sneezing, laughing, or any strenuous activity. Moderate; urinary incontinence with carrying, pushing, lifting, walking, and any light physical activity)

Exclusion Criteria

Pregnancy

Ongoing vulvovaginitis or urinary tract infection or malignancy

Pelvic floor muscle strength is between 0-1 according to the Modified Oxford Scale,

Previous surgery for SUI

Problems with vision or inability to understand given commands

Conservative therapy in the last 6 months

Allergic reaction to the gel used with the perinometer/probe

Evaluations

Evaluation parameters will be applied at the baseline, at the end of 4-weeks treatment program, at the end of 8 weeks treatment program. Outcome measures and applied evaluations are shown in Table 1.

Table 1. Outcome measures and evaluation methods

Primary Outcome Measures	Evaluation Methods
Muscle Strength	-PERFECT Scheme -Surface Electromyography

Secondary Outcome Measures	Evaluation Methods
Symptom Evaluation	-1 hour pad test -The International Consultation on Incontinence Questionnaire-Short Form - Urogenital Distress Inventory- 6 (UDI-6) - Incontinence Impact Questionnaire-7 (IIQ-7) - Overactive Bladder -Validated 8- Question Awareness Tool (OAB-V8)
Patient Satisfaction	Visual Analog Scale (VAS)
Exercise Adherence	VAS Broome Pelvic Floor Muscle Exercise Self- Efficacy Scale
Sexual Function	Female Sexual Function Scale (FSFI)

Treatment Program

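### The Annex 8 adherence VAS is printed with satisfaction labels, so H6 has no unambiguous direct adherence score if the form is used as printed

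*Combined protocol and SAP*

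**What the plan says.** The hypothesis section of the protocol treats satisfaction (H4) and adherence (H6) as separate claims in favour of one-to-one delivery. Table 1 gives adherence its own row among the secondary outcomes, with two instruments: "VAS Broome Pelvic Floor Muscle Exercise Self- Efficacy Scale".

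Both are printed in Annex 8. The VAS stem is "How long did you adhere to the exercise program during your treatment". Below it is a 0-10 line whose lower end reads "Not satisfied at all" and whose upper end carries the corresponding label for high satisfaction. The Broome scale follows in two parts, headed "Part A: How confident are you that you can" and "Part B: How confident are you that pelvic muscle contractions will prevent unwanted urine loss".

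Annex 7, the satisfaction form, prints the same pair of end labels ("Not satisfied at all) (Very satisfied") under each of its three items, for example "How satisfied were you with the treatment you received".

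The Evaluations section sets assessments at baseline, week 4 and week 8 in one general sentence. The SAP compares results at those three times, by ANOVA or Kruskal-Wallis according to distribution.

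**The concern.** A VAS score takes its meaning from the question and the two end labels together. Here the question asks for a duration, the line has no unit of time or proportion, and the labels describe satisfaction. A participant could mark how much exercise she did, how content she is with her own adherence, or how content she is with the programme. The recorded number would not show which.

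At stake is the interpretation of H6. The arms differ in how the sessions are delivered, and satisfaction could respond to that whether or not the amount of exercise does. A between-arm difference on this item could not then be read with confidence as a difference in adherence, nor could its absence be read as equal adherence.

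**Working it through.** No figure in the plan bears on this point, so the check is a comparison of the printed items plus simple counts.

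**1. Do the end labels fit the question?**

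| Item | What the stem asks about | End labels | Fit |
|---|---|---|---|
| Annex 7, item 1 | satisfaction with treatment | satisfaction | yes |
| Annex 7, item 2 | satisfaction with the reduction in complaints | satisfaction | yes |
| Annex 7, item 3 | satisfaction with online follow-up | satisfaction | yes |
| Annex 8, VAS | duration of adherence | satisfaction | no |

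VAS items with this label pair: 3 + 1 = 4. The labels fit 3 of the 4; the exception is the adherence item.

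**2. Could the text extraction have moved the labels?** This is unlikely. Annex 7 has its own three pairs, one under each item. The pair in Annex 8 is a fourth, placed directly under the adherence question and before the Broome scale.

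**3. Does the second instrument supply an adherence score?** Part A has 14 items and Part B has 9, so 14 + 9 = 23. Every item sits under a stem about confidence: in being able to contract the muscles (Part A), or in contractions preventing leakage (Part B). Even the Part A item on contracting three times a day asks how confident the patient is of doing so, not whether she did. This is self-efficacy, which may be related to adherence but is not a record of it.

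**4. Is another adherence measure listed?** Weekly video follow-up is planned, but Table 1 lists no attendance count or exercise log as an outcome. No scoring rule in the text available for review says what the ends of the adherence line mean in terms of exercise done.

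**5. Count of direct scores.** Instruments listed for adherence: 2. Those that ask about adherence: 1 (the VAS). Those that ask about it with end labels that answer the question: 0.

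**6. Can the item be analysed as a change from baseline?** It asks about adherence during treatment already received, and at baseline there has been none. Of the three assessment times, 3 - 1 = 2 (weeks 4 and 8) can yield a meaningful answer.

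**The case against.** The strongest reply is that this is a slip in an English rendering. The English is rough elsewhere in the document, and the form patients complete may have the right labels. The annex title and the stem both say adherence, so many participants would probably answer in that sense. This reply stands as far as effect is concerned: the documents show a printing error but do not show that any patient answered under it. It does not remove the need to check, because the annex is the record of the instrument and nothing in the available text corrects it.

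Several stronger readings are tempting, and the documents do not support them.

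- *The score is worthless, or biased towards one arm.* It is ambiguous rather than empty, and nothing allows a size or direction of bias to be derived.
- *H6 is already measured within H4.* Annex 7 item 3 reads "How satisfied were you that your exercise program is followed by online interviews". Its natural meaning is follow-up by the physiotherapist, not the patient's adherence, so it does not show that the two outcomes overlap.
- *Meaningless baseline answers are scheduled for all four VAS items.* That takes one general sentence literally for every form. The Annex 7 items refer to treatment received, and their wording limits them to later visits.
- *Week 8 recall overlapping week 4 is a flaw.* No recall window is stated, and a cumulative score at the end of treatment is legitimate.
- *The lack of a named test visit is a fault of this item.* The SAP names no variable or visit for any of H1 to H6, so that gap is general.

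**Conclusion.** The concern holds in limited form. As printed, the only listed item that asks about adherence has end labels for a different construct and no time unit, and the other listed instrument measures confidence. H6 therefore has no unambiguous direct adherence score: 0 of 2 listed instruments provide one.

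The reach is one secondary outcome and one of six numbered hypotheses. The primary outcome, muscle strength, is not affected. The conclusion about the printed annex is firm. Any effect on the trial's results depends on an assumption that the documents cannot settle, namely that patients receive the form as printed. The correction is worth making because it is cheap and because H6 depends on this item.

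**What to change.** 1. Compare Annex 8 with the form patients complete, in the language used, and correct the annex whatever the result.
2. If the form matches the annex, make stem and end labels agree in adherence terms. One possible wording: *Since the start of your treatment, how much of the exercise you were asked to do have you done?*, with 0 = none and 10 = all. Other wordings would serve, provided both ends answer the question.
3. Do not pool answers given under the satisfaction labels with answers to the corrected item.
4. State in the SAP that this item is analysed by comparing the arms at post-baseline visits, not as a change from baseline. The SAP's existing choice between parametric and non-parametric tests can be kept.

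The cost is one form correction, one sentence in the SAP, and any ethics notification that a changed patient form requires. No extra visits are needed. The documents do not show whether forms have already been completed; if they have, leaving those answers unpooled reduces the data available for H6. A recall period running from the start of treatment also asks patients to look back over 8 weeks at the final visit.

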Annex 9. Female Sexual Function Index Score

Question	Response Options
Q1: Over the past 4 weeks, how often did you feel sexual desire or interest?	5 = Almost always or always 4 = Most times (more than half the time) 3 = Sometimes (about half the time) 2 = A few times (less than half the time) 1 = Almost never or never
Q2: Over the past 4 weeks, how would you rate your level (degree) of sexual desire or interest?	5 = Very high 4 = High 3 = Moderate 2 = Low 1 = Very low or none at all
Q3. Over the past 4 weeks, how often did you feel sexually aroused ("turned on") during sexual activity or intercourse?	0 = No sexual activity 5 = Almost always or always 4 = Most times (more than half the time) 3 = Sometimes (about half the time) 2 = A few times (less than half the time) 1 = Almost never or never
Q4. Over the past 4 weeks, how would you rate your level of sexual arousal ("turn on") during sexual activity or intercourse?	0 = No sexual activity 5 = Very high 4 = High 3 = Moderate 2 = Low 1 = Very low or none at all
Q5. Over the past 4 weeks, how confident were you about becoming sexually aroused during sexual activity or intercourse?	0 = No sexual activity 5 = Very high confidence 4 = High confidence 3 = Moderate confidence 2 = Low confidence 1 = Very low or no confidence
Q6. Over the past 4 weeks, how often have you been satisfied with your arousal (excitement) during sexual activity or intercourse?	0 = No sexual activity 5 = Almost always or always 4 = Most times (more than half the time) 3 = Sometimes (about half the time) 2 = A few times (less than half the time) 1 = Almost never or never

- Q7: Over the past 4 weeks, how **often** did you become lubricated ("wet") during sexual activity or intercourse?
- 0 = No sexual activity
5 = Almost always or always
4 = Most times (more than half the time)
3 = Sometimes (about half the time)
2 = A few times (less than half the time)
1 = Almost never or never
- Q8: Over the past 4 weeks, how **difficult** was it to become lubricated ("wet") during sexual activity or intercourse?
- 0 = No sexual activity
1 = Extremely difficult or impossible
2 = Very difficult
3 = Difficult
4 = Slightly difficult
5 = Not difficult
- Q9: Over the past 4 weeks, how often did you **maintain** your lubrication ("wetness") until completion of sexual activity or intercourse?
- 0 = No sexual activity
5 = Almost always or always
4 = Most times (more than half the time)
3 = Sometimes (about half the time)
2 = A few times (less than half the time)
1 = Almost never or never
- Q10: Over the past 4 weeks, how **difficult** was it to maintain your lubrication ("wetness") until completion of sexual activity or intercourse?
- 0 = No sexual activity
1 = Extremely difficult or impossible
2 = Very difficult
3 = Difficult
4 = Slightly difficult
5 = Not difficult
- Q11: Over the past 4 weeks, when you had sexual stimulation or intercourse, how **often** did you reach orgasm (climax)?
- 0 = No sexual activity
5 = Almost always or always
4 = Most times (more than half the time)
3 = Sometimes (about half the time)
2 = A few times (less than half the time)
1 = Almost never or never
- Q12: Over the past 4 weeks, when you had sexual stimulation or intercourse, how **difficult** was it for you to reach orgasm (climax)?
- 0 = No sexual activity
1 = Extremely difficult or impossible
2 = Very difficult
3 = Difficult
4 = Slightly difficult
5 = Not difficult
- Q13: Over the past 4 weeks, how **satisfied** were you with your ability to reach orgasm (climax) during sexual activity or intercourse?
- 0 = No sexual activity
5 = Very satisfied
4 = Moderately satisfied
3 = About equally satisfied and dissatisfied
2 = Moderately dissatisfied
1 = Very dissatisfied
- Q14: Over the past 4 weeks, how **satisfied** have you been with the amount of emotional closeness during sexual activity between you and your partner?
- 0 = No sexual activity
5 = Very satisfied
4 = Moderately satisfied
3 = About equally satisfied and dissatisfied
2 = Moderately dissatisfied
1 = Very dissatisfied

- Q15: Over the past 4 weeks, how satisfied have you been with your sexual relationship with your partner?
- 5 = Very satisfied
 4 = Moderately satisfied
 3 = About equally satisfied and dissatisfied
 2 = Moderately dissatisfied
 1 = Very dissatisfied
- Q16: Over the past 4 weeks, how **satisfied** have you been with your overall sexual life?
- 5 = Very satisfied
 4 = Moderately satisfied
 3 = About equally satisfied and dissatisfied
 2 = Moderately dissatisfied
 1 = Very dissatisfied
- Q17: Over the past 4 weeks, how **often** did you experience discomfort or pain during vaginal penetration?
- 0 = Did not attempt intercourse
 1 = Almost always or always
 2 = Most times (more than half the time)
 3 = Sometimes (about half the time)
 4 = A few times (less than half the time)
 5 = Almost never or never
- Q18: Over the past 4 weeks, how **often** did you experience discomfort or pain following vaginal penetration?
- 0 = Did not attempt intercourse
 1 = Almost always or always
 2 = Most times (more than half the time)
 3 = Sometimes (about half the time)
 4 = A few times (less than half the time)
 5 = Almost never or never
- Q19: Over the past 4 weeks, how would you rate your **level** (degree) of discomfort or pain during or following vaginal penetration?
- 0 = Did not attempt intercourse
 1 = Very high
 2 = High
 3 = Moderate
 4 = Low
 5 = Very low or none at all

* For the complete FSFI questionnaire, instructions and scoring algorithm, please see www.FSFIquestionnaire.com, or contact [name] Ph.D., (Department of Psychiatry, UMDNJ-Robert Wood Johnson Medical School, [name])

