The Effectiveness of the Video Conferencing Telerehabilitation Method, Delivered in One on One and Group Sessions, in Urinary Incontinence Cases.

Study Protocol and Statistical Analysis Plan (SAP) (Pages 1 – 21)

November 15,2021

**The Effectiveness of the Video Conferencing
Telerehabilitation Method, Delivered in One on One and Group Sessions, in Urinary
Incontinence Cases.**

Study Protocol (Pages 2-6)

November 15,2021

Study Protocol

Study titled “The Effectiveness of the Video Conferencing Telerehabilitation Method, Delivered in One on One and Group Sessions, in Urinary Incontinence Cases.” was approved by Marmara University Faculty of Medicine Ethical Committee at the meeting on 30.11.2020 with approval number: 1195 (Annex-1).

The legal representatives of the patients who participated in the study will be informed about the aim, duration and the programs to be applied throughout the study. Volunteer Information Form will be signed and approved in accordance with the standards deemed appropriate by the Ethical Committee of Marmara University Faculty of Medicine. The study will be conducted in accordance with the Declaration of Helsinki.

Hypothesis of the Study

H0: With one on one video conference method, exercise training is no superiority of exercise training with group video conferencing method in urinary incontinence.

H1: Exercise training with one on one video conference method is more effective in increasing muscle strength in patients with urinary incontinence.

H2: One on one videoconferencing and exercise training are more effective in reducing the degree of incontinence in patients with urinary incontinence.

H3: Exercise training with one on one videoconferencing method is more effective in increasing the quality of life in patients with urinary incontinence.

H4: Exercise training with one on one videoconferencing method is more effective in increasing patient satisfaction in patients with urinary incontinence.

H5: Exercise training with one on one video conference method is more effective in increasing sexual function in patients with urinary incontinence.

H6: Exercise training with one on one videoconferencing method is more effective in increasing exercise adherence in patients with urinary incontinence.

Randomization of the Study Groups

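### The FSFI scores absence of sexual activity as 0, below the worst function, and the plan does not restrict H5 to sexually active women or say how zeros are handled, so the H5 comparison mixes activity status with function

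*Combined protocol and SAP*

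**What the plan says.** H5 states that one-on-one videoconference training "is more effective in increasing sexual function in patients with urinary incontinence". Table 1 lists the FSFI as the secondary measure of sexual function, and the Evaluations section schedules the evaluations at baseline, week 4 and week 8.

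Annex 9 prints the 19 items with their codes:

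- Q3-Q14 (12 items) include "0 = No sexual activity".
- Q17-Q19 (3 items, on pain) include "0 = Did not attempt intercourse".
- On all 15 of these the worst function is coded 1: for example "1 = Extremely difficult or impossible" on Q8, and "1 = Almost always or always" for pain on Q17 and Q18.
- Q1, Q2, Q15 and Q16 have no zero and start at 1. Q15, for instance, asks "how satisfied have you been with your sexual relationship with your partner".

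The inclusion and exclusion criteria do not mention sexual activity or a partner. The SAP has one general rule, ANOVA or Kruskal-Wallis on the results at the three times. It does not name the FSFI, an analysis set for it, or a treatment of zeros. For the scoring algorithm, Annex 9 refers to an outside source.

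**The concern.** A zero on these items records that nothing happened to be rated. It does not record poor function. Because it sits one step below the worst rating, a total that includes it ranks inactivity beneath severe dysfunction item by item. On the pain items, a woman who did not attempt intercourse scores worse than one who nearly always has pain.

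H5 is a claim about function. If zeros enter the score in an unrestricted population, women who start or stop sexual activity between visits produce large score changes whatever their function does. This widens the spread, so a real effect is harder to detect. Whatever difference is estimated cannot be read as a difference in function. And because the plan states no rule, the analyst could choose one after seeing the data.

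**Working it through.** The plan gives no sample size, power or FSFI effect to reproduce. The item codes below come from Annex 9; everything else is marked as assumed.

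**1. Count.** Q3-Q14 = 12 items and Q17-Q19 = 3 items, so 15 of 19 (79%) carry a zero and 4 do not.

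**2. Score ranges.** Assumption: unweighted sum of the 19 codes, because the documents give no weights.

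- Inactive: zeros on 15 items, 1-5 on the other four, so 4×1 = 4 to 4×5 = 20.
- Active, intercourse attempted: 19×1 = 19 to 19×5 = 95.
- Whole range: 95 − 4 = 91.
- Same level *k* on every answered item: inactive 4*k*, active 19*k*, difference 15*k*. At mid-level (*k* = 3): 57 − 12 = 45 points, and 45/91 = 49% of the range. Over *k* = 1 to 5 the difference is 15 to 75.
- Active without attempting intercourse: zeros on Q17-Q19 only. At *k* = 3 she scores 57 − 9 = 48.

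**3. Added spread.** Assumptions: share *p* inactive, SD 12-15 among active women, SD 3 among inactive women, means 45 apart.

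SD = √[(1−*p*)·SD² + *p*·3² + *p*(1−*p*)·45²]

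- *p* = 0.1, SD 15: √(202.5 + 0.9 + 182.25) = 19.6, or 1.3 times 15.
- *p* = 0.4, SD 12: √(86.4 + 3.6 + 486) = 24.0, or 2.0 times 12.

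**4. Power.** Assumptions: 24 per arm, SD 12, true benefit 8 raw points among active women, baseline correlation 0.6, 10-30% inactive, 5-10% switching status unrelated to arm, baseline-adjusted linear model, 2000 simulated trials per setting.

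| Analysis | Power |
|---|---|
| All women, zeros scored | 18-40% |
| Active at baseline, later zeros still scored | 24-42% |
| Active at both baseline and follow-up | 58-73% |

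The SAP does not specify baseline adjustment. Its rank-based fallback does no better: Kruskal-Wallis on follow-up scores with zeros included gave 16-36%.

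**5. False positives when switching is unrelated to arm.** The same design with no true benefit gave 4.6% (10% inactive, 5% switching) and 5.2% (30% inactive, 10% switching). One mid-level woman resuming activity moves a 24-woman mean by 45/24 = 1.9 points, and two move it by 3.75. With the SDs of 17.7 to 24.0 that step 3 gives for SD 12, the standard error of the difference is SD·√(2/24) = 5.1 to 6.9. Two women therefore shift the difference by less than one standard error.

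**6. False positives when activity changes differ by arm.** Let *d* be the between-arm difference in the net share becoming active, with no change in function. The mean difference shifts by 45*d*: 4.5 points at *d* = 0.10 and 9.0 at *d* = 0.20. Assume a within-arm SD of change of 15, inflated to √[15² + 0.5·*d*(1−*d*)·45²] = 17.8 or 19.7, and two-sided 0.05. The chance of a significant result at 16-32 per arm is then 11-17% for *d* = 0.10 and 25-45% for *d* = 0.20.

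**The case against.** Several points on the other side stand.

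- **The scoring source is not in the documents.** How zeros and domains enter the final score cannot be seen, so every point value above is illustrative. The placement of 0 below 1 is printed in Annex 9 and does not depend on that source.
- **A reader might infer that any inactive woman scores far below the worst-functioning active woman.** The codes do not support this. The ranges meet: 4-20 against a worst active score of 19, so an inactive woman with the best answers on the four remaining items scores one point higher. At mid-level the gap is 19 − 12 = 7 points. The 45-point figure compares an inactive with an active woman, both at mid-level.
- **A reader might infer that one or two women resuming activity by chance would create a false effect.** Step 5 shows otherwise: the extra spread also enters the standard error and the error rate stays nominal. The 11-45% in step 6 needs a real difference between arms in activity, and the documents give no evidence of one.
- **Dropping later zeros is not a clean cure.** Women who contribute a full score at follow-up are then those active at baseline and at that visit, which is selection on behaviour after randomisation. The large power gain in step 4 belongs to that conditional analysis. Restricting by baseline activity alone gains only a little. Resuming activity might also be a benefit of treatment; the simulation treats it as noise.
- **No sentence says that H5 will be tested in all participants.** That follows from the absence of any restriction in H5, the eligibility criteria and the SAP.

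None of this supplies the missing rule.

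**Conclusion.** The point holds in this form: as written, the plan lets activity status enter the FSFI comparison as though it were function, on 15 of 19 items. The expected harm is a 1.3- to 2.0-fold larger SD, power of 18-40% where 58-73% is reached in women active at both visits, and an estimate that cannot be read as sexual function alone. These sizes rest on the raw sum and on assumed sample size, SDs, benefit, correlation, inactivity and switching rates, none of which the documents give. Inflated type I error is not a general consequence; it arises only if changes in activity differ by arm. H5 is a secondary hypothesis, so the primary outcome of muscle strength is unaffected. The SAP should be changed, but the defect does not threaten the trial as a whole.

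**What to change.** Add to the SAP:

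1. H5 is tested in women who report sexual activity on the baseline FSFI, for example a non-zero answer on at least one of Q3-Q14. This set is fixed before randomisation, provided the baseline form is completed first, and the SAP should say so. Women who are inactive at baseline and later resume cannot then drive the result.
2. The number sexually active at baseline, week 4 and week 8 is reported by arm, so that any effect on activity itself is visible.
3. Follow-up results are shown both with zeros scored and with zeros treated as not applicable. The second uses domain scores, so that a woman with zeros only on Q17-Q19 still contributes her other domains. It is labelled as conditional on activity after randomisation and does not stand alone as the main result. The SAP names in advance which version carries the H5 p-value.
4. The analysis of all women with zeros scored is kept as a sensitivity analysis.
5. The scoring algorithm is written out, not only referenced.

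The cost is a few sentences and no new data, because the FSFI already records activity. The downside is fewer women in the H5 analysis and a conclusion limited to those active at baseline. Women who later become inactive remain a problem that the paired presentation discloses but does not remove.
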